1.2 SCHEMA

1.3 SCHEDULE OF ACTIVITIES (SOA)

Procedures	Screening Day -42 to 1	Baseline Day -35 to 1	Day 1	Day 3 (+/- 1 day)	Day 5 (+/- 1 day)	Day 7 (+/- 1 day)	Day 10 (+/- 1 day)	Day 12 (+/- 1 day)	Day 14 (+/- 1 day)	Day 17 (+/- 1 day)	Week 3 (+/- 1 day)	Week 4 (+/- 3 days)	Week 6 (+/- 3 days)	Week 8 (+/- 3 days)	Week 10 (+/- 3 days)	Week 12 (+/- 3 days)	Month 6 (+/- 14 days)	Month 9 (+/- 7 days)	Month 12 (+/- 7 days)	Month 15 (+/- 7 days)	Final Study Visit Month 18 (+/- 7 days)
Informed consent	X																				
Physical exam (including height and weight)		X																			
Medical history	X	X																			
Urine Collection		X															X		X		X
Stool Collection		X ^{5,6}			X ⁵						X ⁵					X ⁶	X ⁵	X ^{5,6}	X ^{5,6}		
CBCD/Plts	X																				
Chemistry Panel ³	X																				
T Cell Panel	X	X							X												X
PT/PTT	X																				
HIV antibody	X																X		X		X
YF Neutralizing Ab	X		X	X	X	X	X				X			X							X
Luminex		X								X						X			X		X
LN Biopsy	X									X											
YF Vaccine			X																		
Leukapheresis ⁸		X																	X		
PBMC/Plasma Storage	X ¹	X		X	X	X	X	X	X	X ⁴	X	X	X	X	X	X	X	X	X	X	X
Serum or urine pregnancy test ²	X	X			X			X			X	X						X			
COVID-19 screening ⁷	X	X	X	X	X	X	X	X	X	X	X	X	X	X	X	X	X	X	X	X	X
AE Assessment		X	X	X	X	X	X	X	X	X	X	X	X	X	X	X	X	X	X	X	X

1. Plasma to screen for absence of yellow fever antibodies
 2. For females of childbearing potential
 3. Chemistry Panel to include Albumin, ALT, AST, Alk. Phosphate, Bilirubin (total), Calcium, Chloride, CO2, Creatinine, Glucose, Potassium, Protein (total), Sodium, Urea Nitrogen
 4. This blood draw will be 60 cc for research
 5. Samples will go to the [name] lab
 6. Samples will go to the [name] lab
 7. Verbal screening related to symptoms and recent exposures (see SOP for details)
 8. Large volume blood draw (60 cc) will be done if a participant is not eligible for leukapheresis

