YFV antibody responses were blunted and of short duration. Titers of neutralizing antibodies to YF were measured by plaque reduction assay (PRA). Initially we compared the week 2 samples between Group 1 and Group 3 using a PRA assay with a lower limit of detection of 10 plaque forming units (pfu) and found only a few of the Ugandans had detectable antibodies whereas most of Group 3 had detectable antibodies ($p < 0.0001$, **Fig. 5A**). We point out that we only had access to plasma samples from Group 3

at the 2 time-points (i.e., D0 and W2) and LN biopsies were not done in that study, so our comparative analysis of antibody formation and decay between these two groups is limited. However, as described below there are historical controls that can be used with Group 1 to make relevant comparisons about peak titer and decay rate(12). We next studied the longitudinally collected plasma samples from Group 1 using a PRA assay with a limit of detection of 100 pfu. We switched to a PRA with a higher threshold of detection titer because the lab performing the first analysis was no longer available to us. We did not duplicate the analysis between Group 1 and 3 as there was limited sample available. Peak titer was seen at the week 3 time-point with a 1.3 log range and a median decrease of 0.9 log by week 60 (Fig. 5B).

These response rates and decay characteristics are similar to those reported by Muyanja in a similar group of Ugandans (12) (and personal communication [name], 2017). Given the variable response in antibody formation and the anatomic changes we found in Ugandan LN, we looked for an anatomic correlate of poor vaccine response and found that measures of the FRCn correlated to the peak antibody titer; the more FRCn, the higher the peak titer of antibodies ($p = 0.02$, Fig. 5C).

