4 STUDY DESIGN

4.1 OVERALL DESIGN

The primary aim of this study is to determine the difference between antibody titers in the two study groups and study the relationship between endemic infections, IA, the FRCn, and CD4 and CD8 T cell subsets and the magnitude and durability of neutralizing antibody response to YFV in a cohort shown to have elevated IA, a damaged FRCn, and pan T cell depletion and a cohort that does not. This is a single arm, open-label, two cohort study of healthy adults in Kampala, Uganda and in Minnesota, USA. The cohort in Uganda will be 30 adults (15 men and 15 women) and the cohort in Minnesota will be 16 adults (8 men and 8 women). Everyone will be screened to ensure there are no contraindications to receiving YFV (e.g., immunosuppression) or the planned procedures. The inclusion and exclusion criteria are discussed in detail in the protocol that is included in the appendix. Participants will have an inguinal LN biopsy and leukapheresis prior to YFV and another LN biopsy 3 weeks after the vaccine administration. The vaccine will be given in the contralateral thigh from the first LN biopsy so that the second biopsy will be from a draining LN. PBMC and plasma will be collected at regular intervals over the 18-month follow-up period. Leukapheresis will be done again at the month 6 visit.

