During the COVID-19 pandemic, participants will be screened for COVID-19 symptoms before coming in for their visits. There will also be AE assessments.

Day 17

At Day 17, participants will have a research blood draw of 60 cc. Blood will be collected for yellow fever neutralizing antibody. There will also be an AE assessment. During the COVID-19 pandemic, participants will be screened for COVID-19 symptoms before coming in for their visit.

Week 3

At Week 3, participants will undergo a lymph node biopsy will be stored. Blood will be collected for:

- T cell panel
- Luminex
- PBMC/plasma storage

Females of childbearing potential will have a serum or urine pregnancy test. There will also be an AE assessment. During the COVID-19 pandemic, participants will be screened for COVID-19 symptoms before coming in for their visit.

Weeks 4 through 10

Participants will return every 2 weeks (see SOEs, Sections 1.2 and 1.3) for blood draws for:

- PBMC/plasma storage
- Yellow fever neutralizing antibody (week 8 only)

At Week 4, females of childbearing potential will have a serum or urine pregnancy test. Stool will be collected for microbiome study.

There will also be an AE assessment. During the COVID-19 pandemic, participants will be screened for COVID-19 symptoms before coming in for their visit.

Week 12

Blood will be collected for:

- HIV antibody
- PBMC/plasma storage
- Luminex

Stool and urine will be collected to check for helminths. There will also be an AE assessment. During the COVID-19 pandemic, participants will be screened for COVID-19 symptoms before coming in for their visit.

Months 6 through 15

Participants will return quarterly starting Month 6 through Month 18.

Months 6, 9, 12 and 15 participants will have blood collected for PBMC/plasma storage.

Month 6 will have stool will be collected for microbiome study. During the month 6 timepoint, leukapheresis will be performed. Before leukapheresis, females of childbearing potential will have a serum or urine pregnancy test. If a participant is not eligible or unable to tolerate leukapheresis, a large volume blood draw (60 cc) will be done.

At the month 12 visit, participants will have stool and urine collected for helminth check. Stool will be collected for microbiome study, and blood will be collected for:

- HIV antibody
- Luminex
- PBMC/plasma storage

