9.4.3 ANALYSIS OF THE SECONDARY ENDPOINT(S)

Differences in rate of YFV antibody titer decay will be compared between vaccinated Ugandans and Minnesotans using linear mixed effects regression model with measurement time, country, and the interaction between measurement time and country as predictors. Baseline LN measures (area with collagen, area with desmin staining, frequency and size of B cell follicles, and frequency of Tfh cells) will be compared between the two countries using Mann-Whitney U tests.

We will examine the association between vaccine response over time and baseline LN measures using linear mixed effects models adjusting for measurement time and gender.

To examine differences in infection patterns between the two countries, we will perform principal component analyses on the baseline pathseq data. We will test for differences in infection patterns between Uganda and the US populations using logistic regression with country as the outcome and the scores for each of the first five principal components as predictors. Differences in helminth infections between Ugandans and Minnesotans will be compared using Fisher's exact test.

We will examine the association between infection history and baseline LN architecture by fitting separate linear regression models for each measure of baseline LN architecture with gender and the 5 pathseq principal component scores as predictors. The association between helminth infections and baseline LN architecture measures will be assessed using Mann-Whitney U tests.

To elucidate the role of previous infections on inflammation and activation we will use sparse canonical correlation analysis (Reference: Witten, D., Tibshirani, R., & Hastie, T. (2009). A penalized matrix decomposition, with applications to sparse principal components and canonical correlation analysis. *Biostatistics*, 10(3), 515-534.) to identify sets of organismal sequences correlated with baseline measures of systemic and lymphatic inflammation (plasma cytokines, frequency of TGF β + and TNF+ cells in lymphoid tissues) and immune activation (Ki67+ and CD69 + cells). The association between helminth infection and measures of inflammation and activation be assessed using a logistic lasso regression model. Measures which have non-zero coefficients in the model will be considered associated with helminth infection.

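### No neutralizing titer is scheduled between Week 8 and Month 18, so the decay comparison rests almost entirely on one late sample, although plasma is banked at six visits in between

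*Combined protocol and SAP*

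**What the plan says.** Durability is part of what the trial sets out to study. Sections 1.1, 3 and 4.1 all name "the magnitude and durability of neutralizing antibody response to YFV". Section 9.1 has hypotheses on the rate of antibody decay, and 9.4.3 states: "Differences in rate of YFV antibody titer decay will be compared between vaccinated Ugandans and Minnesotans using linear mixed effects regression model". The predictors are time, country and their interaction.

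The two schedules place the late titers identically:

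- **Section 8.2.** Weeks 4 to 10 list "Yellow fever neutralizing antibody (week 8 only"). Week 12 lists HIV antibody, storage and Luminex. After that, "Months 6, 9, 12 and 15 participants will have blood collected for PBMC/plasma storage", with HIV antibody and Luminex added at Month 12. The neutralizing titer returns at Month 18.
- **Section 1.3.** The row "YF Neutralizing Ab" is marked at Week 8 and Month 18 and blank at Weeks 10 and 12 and Months 6, 9, 12 and 15. The row "PBMC/Plasma Storage" is marked at all six of those visits.

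Section 7.2 says that participants who withdraw after vaccination are not replaced. Section 9.4.3 says that missing data are not imputed and sets alpha at 0.01 for secondary analyses. In the preliminary study (2.2), "Peak titer was seen at the week 3 time-point with a 1.3 log range and a median decrease of 0.9 log by week 60".

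**The concern.** A decay rate needs titers spread over the period of decay. Here the samples will exist, but the plan uses only the two ends of a 70-week interval. Three things follow.

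1. An early loss followed by a plateau cannot be told from a steady fall. Those are different answers to a durability question.
2. One sample per person fixes that person's slope almost completely.
3. A participant without a Month 18 sample contributes no titer after Week 8, whatever was collected in between.

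If the stored plasma is titrated later without a plan, the result is a post hoc addition to a comparison that is otherwise prespecified.

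**Working it through.** **Plan's own figure.** The only power statement (9.2) is for peak titer: over 85% by a t calculation and 0.871 by Mann-Whitney simulation in the normal case. With 30 vs 16, a difference of 1 log and SD 1, the noncentral t gives 0.884 and a Mann-Whitney simulation 0.861. The figure reproduces to within simulation error and does not depend on the titer gap. No precision or power is given for decay.

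**Inputs.** From the documents: visit times, and 30 Ugandan and 16 US participants. Taken as weeks: Month 6 = 26, Month 12 = 52, Month 18 = 78. Assumed, because the documents give none: residual SD σ of 0.2 to 0.5 log, between-person slope SD τ of 0 to 0.4 log/year, and dropout of 10% to 30%.

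**1. Gap.** 78 − 8 = 70 weeks. From Week 3 to Month 18 is 75 weeks, so 70/75 = 93% of the interval has no titer.

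**2. Leverage of Month 18.** The share is (t − mean)² / Sxx, and the hat value is 1/n plus that share.

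- Weeks 3, 8, 78: mean 29.67, Sxx = 711.1 + 469.4 + 2336.1 = 3516.7. Share 2336.1/3516.7 = 66%; hat value 0.333 + 0.664 = 0.998.
- Adding Months 6 and 12 (3, 8, 26, 52, 78): mean 33.4, Sxx = 3959.2. Share 1989.2/3959.2 = 50%; hat value 0.70.
- Adding Months 6, 9, 12 and 15: Sxx = 4791.4. Share 32%; hat value 0.465.

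Section 8.2 lists a titer at Day 17 but not at Week 3. With Day 17 in place of Week 3 the current share is again 66%.

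**3. Shape.** Assume a total fall of 0.9 log (the size reported by week 60) between Week 3 and Month 18. Compare a steady fall with a fall completed by Month 6.

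| | Steady | Complete by Month 6 | Difference |
|---|---|---|---|
| Week 8 | 0.9 × 5/75 = 0.06 | 0.9 × 5/23 = 0.20 | 0.14 |
| Month 6 | 0.9 × 23/75 = 0.28 | 0.90 | 0.62 |
| Month 18 | 0.90 | 0.90 | 0 |

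At the scheduled titers the two courses differ by at most 0.14 log, which is below the assumed residual SD. At Month 6 they differ by 0.62 log.

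**4. Participants with a late titer.** Assume dropout d spread evenly from Week 12 to Month 18. At present 46 × (1 − d) have a titer after Week 8. With Months 6 and 12 added, only those who leave before Week 26 have none, a fraction (26 − 12)/(78 − 12) = 0.212 of dropouts, which leaves 46 × (1 − 0.212d).

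| Dropout | Current plan | Months 6 and 12 added |
|---|---|---|
| 10% | 41 | 45 |
| 20% | 37 | 44 |
| 30% | 32 | 43 |

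Someone with only Weeks 3 and 8 has Sxx = 12.5, against 3516.7 with Month 18. The residual part of that person's slope variance is about 281 times larger.

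**5. Precision of the country difference in slope, no dropout.** Variance = (σ²/Sxx + τ²)(1/30 + 1/16). Detectable difference at alpha 0.01 and 80% power = (2.576 + 0.842) × SE.

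- Current plan: 0.19 to 0.63 log/year over the assumed σ and τ.
- Months 6, 9, 12 and 15 added: 0.16 to 0.58 log/year, a gain of about 2% to 14%. The upper end is 1 − √(3516.7/4791.4).
- Months 6 and 12 only: at most 1 − √(3516.7/3959.2) = 5.8% (τ = 0), falling to about 1% (σ = 0.2, τ = 0.4).

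**The case against.** The strongest reply is that the planned model is linear in time, and for a linear slope widely separated points are efficient. High leverage at Month 18 is then not a defect in itself, and step 5 shows little precision to be gained. The sole primary endpoint, its hypothesis, its test and its power all concern peak titer; decay is secondary, and 9.1 poses no hypothesis about curve shape. Month 18 does measure persistence directly. The loss is also recoverable. Pathseq and the YF-specific IgM and IgG subclasses are analyzed in 9.4.3 without a row of their own in 1.3, so some assays evidently run on stored samples, and the preliminary study titrated longitudinally collected plasma.

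Most of this stands, and it limits the weight of the point. It does not remove it. Efficiency for a straight line presumes that decay is straight, which the scheduled titers cannot check. The mixed model will use incomplete participants without imputation, but it cannot supply late titers that were never run. The restriction to Week 8 is explicit, and nothing commits to assaying the later plasma. Some other rows of 1.3 disagree with 8.2 (leukapheresis, second biopsy, early titers), but the text of 8.2 establishes this gap alone.

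A reader might infer more, without support:

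- **That Day 3 and Day 5 assays are wasted and could pay for the late ones.** Section 2.2 reports that "only a few of the Ugandans had detectable antibodies", but that is at week 2, and the same sentence says that most US vaccinees were detectable. No Day 3 or Day 5 titers and no assay costs are given.
- **That titers will hit an assay floor before Month 18.** The limit of 100 belongs to the earlier assay; this trial's limit is not stated. Nor is the base of the log in 9.2, so the share below 100 cannot be fixed.
- **That boosts from re-exposure or re-vaccination will be missed.** The documents report neither during follow-up. HIV acquisition is likewise a reason for which an investigator may withdraw someone, not an automatic loss.

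**Conclusion.** The point holds as a gap in prespecification that is worth closing. Both schedules leave about 70 weeks without a neutralizing titer, and the between-country decay comparison therefore rests almost entirely on Month 18. What is lost is the shape of decay and the late information on anyone who misses that visit: 5, 9 or 14 of 46 participants at the assumed dropout rates, against 1, 2 or 3 with Months 6 and 12 added.

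The head counts rest on assumed dropout, the precision figures on assumed SDs, and the shape example on an assumed 0.9 log fall over the whole interval; the gap and the leverage follow from the visit times alone. It would go too far to say that the decay comparison is invalid or that the primary analysis is compromised: a linear slope remains estimable, and peak titer is untouched.

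**What to change.** - **In 8.2 and the Schedule of Activities:** prespecify the YF neutralizing assay on the banked Month 6 and Month 12 plasma, and on Months 9 and 15 if affordable. Run these alongside the same person's other post-vaccination samples, so that differences between assay runs do not enter the slope.
- **In 9.4.3:** let the decay model take a non-linear time term, for example a change in slope at Month 6, with its own interaction with country. With the current titers the early slope in such a model would come from a five-week span.

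Cost: 46 × 2 = 92 assays (46 × 4 = 184 with all four months) and a wording change. No new visits, blood draws or participants are needed. The return is curve shape and retained participants rather than a much smaller standard error. The early titers can stay as scheduled; where 1.3 and 8.2 differ on them (Week 3 against Days 12, 14 and 17), the two should be reconciled in the same amendment.

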8.3 ADVERSE EVENTS AND SERIOUS ADVERSE EVENTS

8.3.1 DEFINITION OF ADVERSE EVENTS (AE)

Adverse event means any untoward medical occurrence associated with the use of an intervention in humans, whether or not considered intervention-related (21 CFR 312.32 (a)).

8.3.2 DEFINITION OF SERIOUS ADVERSE EVENTS (SAE)

An adverse event (AE) or suspected adverse reaction is considered "serious" if, in the view of the investigator, it results in any of the following outcomes: death, a life-threatening adverse event, inpatient hospitalization or prolongation of existing hospitalization, a persistent or significant incapacity or substantial disruption of the ability to conduct normal life functions, or a congenital anomaly/birth defect. Important medical events that may not result in death, be life-threatening, or require hospitalization may be considered serious when, based upon appropriate medical judgment, they may jeopardize the participant and may require medical or surgical intervention to prevent one of the outcomes listed in this definition. Examples of such medical events include allergic bronchospasm requiring intensive treatment in an emergency room or at home, blood dyscrasias or convulsions that do not result in inpatient hospitalization, or the development of drug dependency or drug abuse.

8.3.3 CLASSIFICATION OF AN ADVERSE EVENT

8.3.3.1 SEVERITY OF EVENT

Toxicity and adverse events will be classified according to Division of AIDS (DAIDS) Table for Grading the Severity of Adult and Pediatric Adverse Events, Corrected Version 2.1. A copy of this can be downloaded from the DAIDS home page at <https://rsc.niaid.nih.gov/sites/default/files/daidsgradingcorrectedv21.pdf>

AE/SAE Grading Assignment

All adverse events will be graded in the following manner:

- Grade 1 (Mild): Events require minimal or no treatment and do not interfere with the participant's daily activities.
- Grade 2 (Moderate): Events result in a low level of inconvenience or concern. Moderate events may cause some interference with functioning.
- Grade 3 (Severe): Events interrupt a participant's usual daily activity and may require systemic drug therapy or other treatment. Severe events are usually incapacitating.

- Grade 4 (Life-threatening): Any adverse drug experience that places the participant, in the view of the investigator, at immediate risk of death from the reaction as it occurred (i.e., it does not include a reaction that had it occurred in a more severe form, might have caused death).
- Grade 5 (Death)

8.3.3.2 RELATIONSHIP TO STUDY INTERVENTION

All adverse events (AEs) must have their relationship to study intervention assessed by the clinician who examines and evaluates the participant based on temporal relationship and his/her clinical judgment. The degree of certainty about causality will be graded using the categories below. In a clinical trial, the study product must always be suspect.

- **Related** – The AE is known to occur with the study intervention, there is a reasonable possibility that the study intervention caused the AE, or there is a temporal relationship between the study intervention and event. Reasonable possibility means that there is evidence to suggest a causal relationship between the study intervention and the AE.
- **Not Related** – There is not a reasonable possibility that the administration of the study intervention caused the event, there is no temporal relationship between the study intervention and event onset, or an alternate etiology has been established.

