The risks of the lymph node biopsy are bleeding, infection, seroma, and scarring. Any participant who develops a seroma will have it drained with a syringe in the clinic. These complications are rare. All post-operative and post-biopsy care will be provided by study nurses. Participants will be monitored for a minimum of 4 hours post-surgery prior to being allowed to return home. If complications occur, the participant will be seen immediately by a qualified surgeon.

Leukapheresis

The risks of the apheresis process include bruising and/or bleeding in the arms when needles are placed for the apheresis; a reaction to the drug used as an anticoagulant during the procedure, citrate; and loss of blood, especially platelets. Rarely, veins cannot be found to insert the needles a catheter must be placed in a large neck vein to collect the cells.

Blood Draw

Events associated with venipunctures include discomfort, slight bruising, bruising, bleeding, lightheadedness, fainting, infection at the venipuncture site, nausea, anxiety and swelling at the venipuncture site.

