6 STUDY INTERVENTION

There are no study interventions and the following information is provided as they are central to the study. Stamaril and YF-VAX are the manufacturers and both can be used at either study site.

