8.4 UNANTICIPATED PROBLEMS

8.4.1 DEFINITION OF UNANTICIPATED PROBLEMS (UP)

The Office for Human Research Protections (OHRP) considers unanticipated problems involving risks to participants or others to include, in general, any incident, experience, or outcome that meets all of the following criteria:

- Unexpected in terms of nature, severity, or frequency given (a) the research procedures that are described in the protocol-related documents, such as the Institutional Review Board (IRB)-approved research protocol and informed consent document; and (b) the characteristics of the participant population being studied;
- Related or possibly related to participation in the research ("possibly related" means there is a reasonable possibility that the incident, experience, or outcome may have been caused by the procedures involved in the research); and
- Suggests that the research places participants or others at a greater risk of harm (including physical, psychological, economic, or social harm) than was previously known or recognized.

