9.4.4 SAFETY ANALYSES

Any AEs will be reported annually in a study report that will document AEs and completeness of data. This report will include the total number of AEs for each cohort and the total number of participants in each cohort that experience an AE. AEs will be summarized in terms of severity and relatedness and the number of participants experiencing SAEs will also be reported for each cohort. A line listing will also be included in this report.

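### The AE causality scale has no category for study procedures and its two codes overlap, so biopsy and leukapheresis harms cannot be identified from the relatedness summary

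*Combined protocol and SAP*

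**What the plan says.** **Target of the assessment.** Section 8.3.3.2 requires: "All adverse events (AEs) must have their relationship to study intervention assessed by the clinician who examines and evaluates the participant". It adds: "In a clinical trial, the study product must always be suspect". Section 8.3.4 lists what is collected for each event, and the only causality item there is the relationship to the study product.

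**What the intervention is.** The synopsis (Section 1.1) fills its study-intervention row with the yellow fever vaccine. Section 6 opens: "There are no study interventions and the following information is provided as they are central to the study".

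**The two codes.** Each definition in Section 8.3.3.2 is a list of alternatives. The Related list includes "or there is a temporal relationship between the study intervention and event". The Not Related list ends "or an alternate etiology has been established".

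**The procedures.** Section 4.1 plans a biopsy and a leukapheresis before vaccination, a second biopsy three weeks after it, and a second leukapheresis at month 6. Section 2.3.1 lists their hazards separately from those of the vaccine: "The risks of the lymph node biopsy are bleeding, infection, seroma, and scarring". For leukapheresis it lists bruising or bleeding, citrate reaction and loss of blood, especially platelets.

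**What is reported.** Section 9.4.4 gives counts by cohort and says "AEs will be summarized in terms of severity and relatedness". It adds a line listing without naming its columns.

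**A different standard elsewhere.** For unanticipated problems, Section 8.4.1 asks whether the event may have been "caused by the procedures involved in the research".

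**The concern.** The study gives a licensed vaccine and adds invasive procedures done for research. Section 2.3.2 anticipates no benefit to participants. Section 5.5 recruits some Minnesota participants through travel-clinic appointments for this vaccine, so for them the procedures are the added research risk. A safety summary for such a study should let a reader separate three kinds of event: vaccine reactions, procedure harms and incidental illness.

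The planned summary has two classes, both defined against the vaccine. A procedure harm coded Not Related is pooled with incidental illness. A procedure harm after vaccination may be coded Related or Not Related, depending on which alternative the assessor applies. The report compares two cohorts at two sites, so a difference in coding habit would look like a difference in safety.

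Two other parts of the protocol call for the missing attribution. Section 8.4.1 judges unanticipated problems against research procedures. The Ugandan insurance described in Section 8.3.4 covers injury from procedures as well as from the study medication. Section 8.3.3.3 has the same gap: it defines expectedness against risk information for the study intervention, so read literally a biopsy seroma is unexpected even though Section 2.3.1 lists it.

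**Working it through.** The plan gives no figure to reproduce here. The check has two parts: the logic of the codes and a count of planned exposures.

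**1. Do the codes exclude each other?** Write the criteria of Section 8.3.3.2 as yes/no items:

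- K: the event is known to occur with the intervention
- R: there is a reasonable possibility that the intervention caused it
- T: there is a temporal relationship
- A: another etiology is established

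Then Related = K or R or T, and Not Related = (not R) or (not T) or A.

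Four items give 2 × 2 × 2 × 2 = 16 combinations:

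| Result | Condition | Combinations |
|---|---|---|
| Related only | R and T hold, A does not; K either way | 2 |
| Not Related only | none of K, R, T holds; A either way | 2 |
| Both | all others | 16 − 2 − 2 = 12 |
| Neither | none | 0 |

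Some of the 16 are clinically implausible. Suppose K implies R and R implies T. Then (K, R, T) can only be 000, 001, 011 or 111, and with A either way this leaves 4 × 2 = 8 combinations. Of these, 2 are Related only (011 and 111 without A), 2 are Not Related only (000), and 4 are both (001 with or without A, 011 with A, 111 with A). The overlap survives the restriction. These counts show that the rule contradicts itself; they do not estimate how often events will fall in the overlap.

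**2. Worked events.**

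- *Wound infection after the first biopsy, before vaccination.* T and R fail. The code is Not Related. That is correct for the question asked, but the event is then indistinguishable from incidental illness.
- *Seroma after the Week 3 biopsy.* It follows the vaccine by about three weeks. If the assessor accepts T, it is Related. The biopsy is an established cause, so A holds and it is also Not Related.
- *Citrate reaction at the month 6 leukapheresis.* A holds. Whether T holds is left to the assessor, because Section 8.3.3.2 gives no time window.

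**3. Planned exposures (Section 4.1).** Participants: 30 + 16 = 46.

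| Exposure | Calculation | Number |
|---|---|---|
| Vaccine doses | 46 × 1 | 46 |
| Biopsies | 46 × 2 | 92 |
| Leukaphereses | 46 × 2 | up to 92 |
| Procedures in total | 92 + 92 | up to 184 |
| Before vaccination | 46 + 46 | up to 92 |
| After vaccination | 46 + 46 | up to 92 |

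The leukapheresis count is a maximum because Section 8.2 allows a 60 cc blood draw instead. Other scheduled blood draws are not counted.

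**The case against.** The safeguards are real. Section 8.3.4 records every event from consent onward whatever its relationship, and Section 9.4.4 counts all of them by cohort. Under Section 10.1.5 both independent safety monitors review all adverse events, can open participant records in real time, and write a report on each serious event. The form collects a description and an onset time, so an inguinal seroma dated just after the Week 3 biopsy would be recognisable in the line listing. Section 8.3.3.2 also calls for clinical judgment, and a careful clinician would often settle a plain surgical complication as Not Related. Safety is not an endpoint in Section 3, and Section 2.3.1 calls biopsy complications rare.

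These points rule out three stronger readings that a reader might draw:

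- *Procedure harms are coded to the wrong cause.* The plan has no cause field, and Not Related to the vaccine is the right answer for a harm that precedes it. Attribution to the vaccine is possible only after vaccination, and it is not certain.
- *Procedure harms are under-reported.* No event is omitted; what is missing is the label.
- *The monitors cannot judge the procedures.* They can, case by case, from records and the listing.

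The objection does not remove the defect. Reconstruction from a listing with unspecified columns does not replace attribution by the clinician who saw the participant. Clinical judgment is not given precedence over the listed alternatives, and the instruction always to suspect the product pulls the other way. The unanticipated-problem definition covers only events that are also unexpected and suggest greater risk than was known.

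**Conclusion.** The point holds as a defect in recording and reporting. Relatedness is assessed only against the vaccine, and the two codes are not mutually exclusive. Harms from 92 biopsies and up to 92 leukaphereses therefore cannot be identified from the relatedness summary, and those after vaccination (46 biopsies and up to 46 leukaphereses) may be coded inconsistently, most clearly after the Week 3 biopsy.

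The conclusion rests on two assumptions. First, the case report form follows the list in Section 8.3.4; the form itself is not among the documents, so the absence of a procedure field is inferred from that list. Second, all 46 participants complete the planned procedures. The counts are exposures, not events: the documents give no complication rates, so the number of misclassified events cannot be estimated. The primary analysis is not affected.

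**What to change.** 1. In Section 8.3.3.2, the Section 8.3.4 list and the case report form, record relatedness separately for (a) vaccine, (b) lymph node biopsy, and (c) leukapheresis or blood draw.
2. Make the codes exclusive. Related: there is a reasonable possibility of causation, with timing as evidence but not sufficient alone. Not Related: everything else.
3. In Section 9.4.4, tabulate events by cohort and attributed cause, alongside severity.
4. Reconcile the synopsis and Sections 6, 8.3.3.2, 8.3.3.3 and 8.3.4 on what the study intervention is, so that expectedness can also be judged against the procedure risks in Section 2.3.1.

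The cost is a few added fields, a larger annual table, and a protocol amendment that needs IRB review under the Statement of Compliance. Events already recorded would need to be re-rated from source. Clinical care and the efficacy analyses do not change.
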